3.3.1.4 Dose change

Dose delay/interruption: any dose change/delay flagged in the DAR CRF page, satisfying the following criteria:

- a reason other than "as per protocol",
- a zero actual dose,
- occurs between the first and last non-zero doses,
- follows a non-zero actual dose.

Dose reduction: any dose change/delay flagged in the DAR CRF page, satisfying the following criteria:

- a reason other than "as per protocol",
- a non-zero actual dose below the immediate previous non-zero actual dose
- a non-zero actual dose below the treatment assigned as per safety set

Dose increment: any dose change/delay flagged in the DAR CRF page, satisfying the following criteria:

- a reason other than "as per protocol",
- a non-zero actual dose above any previous non-zero actual dose
- a non-zero actual dose above the treatment assigned as per safety set

The following criteria are used to identify an intra-patient dose escalation:

- dose change flag checked with reason "as per protocol"
- planned dose above any previous planned dose.

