1.1 Study design

This is a multi-center, open-label, dose finding, Phase Ib dose escalation study to estimate the MTD(s) and/or RP2D(s) for the combination of LGX818 and MEK162 and triple combination of LGX818 and MEK162 and LEE011, followed each independently by a Phase II part to assess the clinical efficacy and to further assess the safety of the combinations in selected patient populations.

Oral LGX818 and MEK162 will be administered once daily and twice daily, respectively, on a continuous schedule. Oral LGX818 and MEK162 and LEE011 will be administered once daily on a continuous schedule (LGX818), twice daily on a continuous schedule (MEK162) and once daily three week on, one week off (LEE011), respectively. Patient will be treated until progression of disease, unacceptable toxicity develops, or withdrawal of infored consent, whichever occurs first. Continued treatment beyond progression of disease will be allowed under certain circumstances.

Dose escalation (Phase Ib)

The dose escalation part of the trial will be conducted in adult patients with BRAF V600dependent advance solid tumors. This part of the trial is expected to enroll at least 18 patients for the dual combination and at least 12 patients for the triple combination. For the purposes of the dose escalation decisions, each cohort will consist of 3 to 6 newly enrolled patients. The successive cohorts of patients will receive increasing doses of the combinations. The first cohort for the dual combination will be treated with the starting combination doses of 50 mg once daily (qd) for LGX818 and 45 mg twice daily (bid) for MEK162. The first cohort for the triple combination will be treated with the starting combination doses of 200 mg once daily (qd) for LGX818, 45 mg twice daily (bid) for MEK162 and 100 mg once daily (qd) for LEE011 (3 weeks on/1 week off regimen).

Once all patients in a dose cohort have completed 28 days (1 cycle) of treatment and an assessment of their dose limiting toxicity (DLT) status is performed, the adaptive Bayesian logistic regression model (BLRM) will be updated. At each decision time point, the adaptive BLRM provides the upper boundary for the combinations that meet the escalation with overdose control (EWOC) criteria. The clinical synthesis of the available toxicity information,

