3.6.9 Tolerability

Tolerability of study drug treatment will be assessed by summarizing the number of treatment dose interruptions and dose reductions. Reasons for dose interruption and dose reductions will be listed by patient and summarized. Dose interruption occurs when patient receives 0 mg of the study drug.

Version 2.2

Cumulative dose, dose intensity and relative dose intensity of MEK162, LGX818 and LEE011 will be summarized. Categories for relative dose intensity of each study drug will be specified as $< 0.5, \ge 0.5$ to $< 0.75, \ge 0.75$ to $< 0.9, \ge 0.9$ to < 1.1 and ≥ 1.1 . The number and proportion of patients within each category will be presented.

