Table 14.3.6.2.3d	ECG shift table based on notable values by treatment group/arm	Safety Set	Phase Ib/II, Triple Combination
Table 14.3.7.1d	Left ventricular ejection fraction worst CTC grade by treatment group/arm	Safety Set	Phase Ib/II, Triple Combination
Table 14.3.8.1d	WHO/ECOG performance status by treatment group/arm	Safety Set	Phase Ib/II, Triple Combination
Table 14.4.1.1a	Duration of exposure to study drug by treatment group	Safety Set	Phase lb, Dual Combination
Table 14.4.1.1b	Duration of exposure to study drug by arm	Safety Set	Phase II, Dual Combination
Table 14.4.1.1d	Duration of exposure to study drug by treatment group/arm	Safety Set	Phase Ib/II, Triple Combination
Table 14.4.1.2d	Dose reductions of study treatment by treatment group/arm	Safety Set	Phase Ib/II, Triple Combination
Table 14.4.1.3d	Dose delays of study treatment by treatment group/arm	Safety Set	Phase Ib/II, Triple Combination
Table 14.4.1.4a	Summary statistics of exposure of study treatment by treatment group	Safety Set	Phase Ib, Dual Combination
Table 14.4.1.4b	Summary statistics of exposure of study treatment by arm	Safety Set	Phase II, Dual Combination
Table 14.4.1.4c	Summary statistics of exposure of study treatment by treatment group/arm	Safety Set	Phase Ib/II, Dual Combination
Table 14.4.1.4d	Summary statistics of exposure of study treatment by treatment group/arm	Safety Set	Phase Ib/II, Triple Combination
Table 14.4.2.1d	Concomitant medications and significant non-drug therapies started prior to the start of study drug by	Safety Set	Phase Ib/II, Triple Combination

	preferred term and treatment group/arm		
Table 14.4.2.2d	Concomitant medications and significant non-drug therapies started after the start of study drug by preferred term and treatment group/arm	Safety Set	Phase Ib/II, Triple Combination
Table 14.4.2.3a	Antineoplastic therapy since discontinuation of study drug by preferred term and treatment group	Safety Set	Phase lb, Dual Combination
Table 14.4.2.3b	Antineoplastic therapy since discontinuation of study drug by preferred term and arm	Safety Set	Phase II, Dual Combination
Table 14.4.2.3d	Antineoplastic therapy since discontinuation of study drug by preferred term and treatment group/arm	Safety Set	Phase Ib/II, Triple Combination
Table 14.4.4.1.1	Summary of encorafenib concentrations by treatment group	Full Analysis Set	Phase Ib
Table 14.4.4.1.2	Summary of encorafenib concentrations by arm	Full Analysis Set	Phase II

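### Sections 3.3.1.4 and 3.6.9 of the SAP define dose interruption differently, and they disagree on how LEE011's planned week off is counted

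*SAP*

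**What the plan says.** **Schedule.** SAP Section 1.1 gives the third drug of the triple combination as "once daily three week on, one week off (LEE011"). Each 28-day cycle therefore contains a planned week without LEE011.

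**Section 3.3.1.4 (Dose change).** A dose delay/interruption is a change or delay flagged on the dosage administration (DAR) page that meets four criteria together:

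1. the recorded reason is something other than per protocol;
2. the record has "a zero actual dose";
3. it "occurs between the first and last non-zero doses";
4. it "follows a non-zero actual dose".

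The dose-reduction rule in the same section is more precise about position. It asks for "a non-zero actual dose below the immediate previous non-zero actual dose". The delay rule has no such word.

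**Section 3.6.9 (Tolerability).** Tolerability is to be assessed by the number of interruptions and reductions, and the section states: "Dose interruption occurs when patient receives 0 mg of the study drug". It sets no condition on reason or position and does not refer to 3.3.1.4.

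**Output.** Section 4.1.1 lists Table 14.4.1.3d for the triple combination, "Dose delays of study treatment by treatment group/arm".

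**The concern.** One count has two definitions, and they treat a planned rest week in opposite ways. Two programmers could each follow the SAP and deliver different LEE011 interruption counts.

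The fourth criterion of 3.3.1.4 suits continuous dosing, where it stops a run of zero-dose records from being counted more than once. It was not adapted to a schedule with planned zero-dose days. A course withheld at the start of a cycle comes straight after the week off, so the record before the delay may itself be a zero.

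The SAP does adapt to the LEE011 schedule elsewhere: in the last date of exposure (2.1.2.5) and in the minimum exposure for the dose-determining set (2.2, 16 of 21 days). Section 3.3.1 also has a regimen-specific interruption note, but only for twice-daily dosing.

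At stake is the tolerability description of the drug that distinguishes the triple from the dual combination. Safety and tolerability is a secondary objective (Table 1-1).

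**Working it through.** The SAP states no figure on this point, so there is none to reproduce. The check applies each rule as written to short LEE011 record sequences.

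**Inputs**
- The four criteria of Section 3.3.1.4 and the 0 mg sentence of Section 3.6.9.
- The schedule in Section 1.1.
- Two things the SAP leaves open: whether *follows* means the immediately preceding record or any earlier record, and whether the week off is entered as a zero-dose row on the DAR page. Both possibilities are tried.

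**Notation.** D is a dosed period, R a planned week off recorded as a zero-dose row with reason per protocol, and A a zero-dose row with reason adverse event.

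| Records | 3.3.1.4, immediately follows | 3.3.1.4, any earlier dose | 3.6.9, zero-dose rows |
|---|---|---|---|
| (a) D R D: full compliance | 0 | 0 | 1 |
| (b) D R A D: late course start, week off recorded | 0 | 1 | 2 |
| (c) D A D: late course start, week off not recorded | 1 | 1 | 1 |
| (d) D A D R D: mid-course interruption, then normal week off | 1 | 1 | 2 |
| (e) D A R A D: one hold that spans the week off | 1 | 2 | 3 |

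**Step 1: the conflict between sections.** Row (a) shows it with no assumption about the fourth criterion. The planned rest is excluded by the reason criterion of 3.3.1.4 and counted by the 0 mg wording of 3.6.9. A compliant patient with 6 courses has 6 − 1 = 5 rest weeks between the first and last doses. The count is 0 under 3.3.1.4 and 5 under 3.6.9, taking each rest week as one interruption.

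**Step 2: what the fourth criterion can mean.** The third criterion already places the record after the first non-zero dose, so an earlier non-zero dose always exists. If *follows* means any earlier dose, the fourth criterion can remove nothing. Enumeration agrees. Take all sequences of length 3 to 7 built from D, R and A that contain at least one D. Their number is the sum of 3^L − 2^L, which is 19 + 65 + 211 + 665 + 2,059 = 3,019. In none of them did the criterion remove a record. It has a function only if it means immediately follows.

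**Step 3: what that reading does to LEE011.** In row (b) the delay comes straight after a zero-dose rest record, so it fails the fourth criterion: 0 counted, 1 real. In row (c) there is no rest record, the preceding record is a dose, and the delay is counted on either reading. The omission therefore needs both conditions together.

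**Step 4: the restated criterion.** Require that the most recent preceding record, ignoring per-protocol zero-dose records, is a non-zero dose. By hand:
- (a) 0, because no record passes the reason criterion.
- (b) 1, because R is skipped and D precedes A.
- (c) 1.
- (d) 1.
- (e) 1, because the first A counts; for the second, R is skipped and the preceding record is A, a zero.

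Each row gives the number of separate unplanned holds.

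**The case against.** **The delay rule does not say immediately, and the DAR convention is not given.** Both points are correct. The adjacent reduction rule does specify the immediate previous dose, so its absence from the delay rule can be argued to be deliberate. The SAP also never says that the week off is entered as a row. A reader might infer that a LEE011 delay after the week off is never counted. The document does not support that: row (c), and row (b) under the looser reading, count it. The stricter reading remains the more sensible one, since otherwise the criterion does nothing, but the omission is conditional.

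**The working algorithm is in 3.3.1.4, and the 3.6.9 sentence is only a gloss.** This has force. The heading in 3.3.1.4 matches the subject of Table 14.4.1.3d, and 3.6.9 itself asks for reasons for interruption, which fits reason-flagged events. A program that reads only DAR rows would also count rest weeks under 3.6.9 only if they are rows. A reader might infer that the final table will be swamped by rest weeks; the SAP gives no basis for predicting that. Still, 3.6.9 is the section that makes the number of interruptions the tolerability measure, and its stated rule contradicts 3.3.1.4.

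**Missed delays would show elsewhere.** This stands. Withheld LEE011 lowers cumulative dose and relative dose intensity (3.3.1.3), appears in the ribociclib administration listing (16.2.5.1.3), and, when driven by an adverse event, falls within Table 14.3.1.2.5d. The specification of the primary efficacy and dose-limiting toxicity analyses does not use this count. That limits the consequence but does not remove the contradiction.

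**Conclusion.** The point holds in two parts of different strength.

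1. **Firm.** Sections 3.3.1.4 and 3.6.9 conflict for LEE011. Read literally, a fully compliant patient scores 0 under one and one interruption per planned rest week under the other. This follows from the wording and the schedule alone.
2. **Conditional.** The fourth criterion of 3.3.1.4 misses a delay that begins at the end of the week off if *follows* means immediately follows and the week off is a zero-dose DAR record. If either condition fails, the delay is counted. The first condition is the only reading that gives the criterion an effect; the second cannot be settled from the SAP.

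The number of patients affected cannot be estimated from the document; the counts above are illustrations. The effect is limited to descriptive tolerability counts for one of the three drugs. It merits correction because a planned output should not depend on which section is programmed or on an unstated data-entry convention.

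**What to change.** These changes concern counting only and leave dosing untouched.

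- **Section 3.6.9:** delete the 0 mg sentence and refer to 3.3.1.4 as the single definition of delay/interruption, used also for Table 14.4.1.3d.
- **Section 3.3.1.4, fourth criterion:** replace with *the most recent preceding record, ignoring zero-dose records with reason as per protocol (planned rest), is a non-zero actual dose*.

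This works whether or not rest weeks are entered as rows. The look-back must skip the planned-rest record rather than accept it as a valid predecessor. If a per-protocol zero were accepted, the hold in row (e) would count as two delays.

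Cost: two sentences of SAP text and a small derivation change, with no new data. The reported number of LEE011 delays may rise.

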3.3.2 Concomitant medication

The Safety set will be used for all below mentioned concomitant medication tables.

Concomitant therapy is defined as all interventions (therapeutic treatments and procedures) besides the study treatment that were administered to a patient preceding or coinciding with the study assessment period.

Concomitant medications entered into the database will be coded using the WHO Drug Reference List (WHODRUG 19SEP2014, version 4.3) to allow for categorization by

preferred term and by ATC class (note that a medication/therapy can appear with more than one ATC class).

Concomitant medications and significant non-drug therapies taken concurrently with the study treatment will be listed and summarized by ATC class, preferred term by contingency tables. These summaries will include medications starting on or after the start of study treatment or medications starting prior to the start of study treatment and continuing after the start of study treatment.

Any prior concomitant medications or significant non-drug therapies starting and ending prior to the start of study treatment will be listed.

Further anti-neoplastic therapies administered concomitantly with study treatment will be listed based on their identification (by the method given in Section 3.2.5) by the protocol deviation process.

Anti-neoplastic therapies since discontinuation of study drug will be listed and tabulated by ATC class and preferred term.

Concomitant medications with a possible PK interaction with LGX818, MEK162 and LEE011 will be identified prior to database lock and listed:

• Inhibitors, inducers and/or substrates of CYP2B6, CYP2C9, CYP3A4, UGT1A1, P-gp, BCRP, OAT1, OAT3, OCT1, OCT2, OATP1B1, OATP1B3, CYP1A2 and CYP2C19 will be identified, classified and listed.

See [CMEK162X2110 Protocol Appendix 14-.4] for complete list of inhibitors, inducers and substrates which might interact with LGX818 and MEK162 and LEE011.

3.4 Analysis of the primary variable(s)

3.4.1 **Primary variable(s)**

3.4.1.1 Phase lb

Estimation of the MTD of the combination treatment will be based upon the estimation of the probability of DLT in Cycle 1 for patients in the DDS. This probability is estimated by the model in Section 3.4.2.1. Note that more than one dose-combination of dual combination (LGX818 and MEK162) or triple combination (LGX818 and MEK162 and LEE011) may be identified as a MTD, and more than one RP2D may be established for further evaluation in the phase II part of the study.

The dose determining set (DDS) will be used for all dose determining analyses.

3.4.1.2 Phase II

Dual combination (LGX818 and MEK162)

For arm 1, the primary variable is the Disease Control Rate (DCR) at week 16. Estimation of the true DCR using a Bayesian design as described in the protocol will not be performed for

the CSR. Instead, the observed DCR for patients in the FAS will be presented. The primary analysis of the DCR will be based on the local review of overall lesion responses.

For arms 2 + 3, the primary variable is the Objective Response Rate (ORR), defined as the proportion of patients with a best overall response of complete response (CR) or partial response (PR). Estimation of the true ORR using a Bayesian design as described in the protocol will not be performed for the CSR. Instead, the observed ORR for patients in the FAS will be presented. The primary analysis of the ORR will be based on the local review of overall lesion responses.

Triple combination (LGX818 and MEK162 and LEE011)

For arm A, the primary variable is the Objective Response Rate (ORR). Estimation of the true ORR using a Bayesian design as described in the protocol will not be performed for the CSR. Instead, the observed ORR for patients in the FAS will be presented. The primary analysis of the ORR will be based on the local review of overall lesion responses.

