An initial interim CSR will be prepared based on all Phase Ib/Phase II patient data from the dual study drug combination. The cut-off for reporting will be either LPFV + 18 months or when 80% of the patients can be assessed for progression free survival (PFS), whichever occurs first. Additional data for patients continuing to receive the MEK162 and LGX818 dual combination beyond the cutoff point for the initial reporting, as allowed by the protocol, and the Phase Ib/II data from the LGX818 and MEK162 and LEE011 triple combination will be summarized in a final CSR once all patients have discontinued the study. Although this SAP provides comprehensive detail on analyses performed throughout the lifetime of the study, only analyses included in the appendices for the final CSR (Section 4: Final Analysis Appendices) will be performed for the final analysis. For the presentation of results in the final analysis, LGX818, MEK162, and LEE011 will be referred to by their respective generic names: encorafenib, binimetinib, and ribociclib.

In this document, the dual and triple combination refers to the combination of LGX818 and MEK162, and LGX818 and MEK162 and LEE011, respectively, when not specified.

The purpose of the CSRs is to report the estimated maximum tolerated dose (MTD) and/or recommended phase II dose (RP2D), characterize the dose limiting toxicities (DLT), safety profile and efficacy of LGX818/MEK162 and LGX818/MEK162/LEE011 combinations in patients with solid tumors harboring a BRAF V600 mutation.

In addition, the CSR also report the assessment of clinical efficacy and safety of the LGX818 and MEK162 combination in patients with BRAF V600 mutant metastatic colorectal cancer (mCRC), patient with BRAF V600 mutant metastatic melanoma, who have progressed after prior selective BRAF inhibitor and patient with BRAF V600 mutant metastatic melanoma, who are naïve to prior selective BRAF inhibitor treatment.

[figure not shown]
An interim analysis is planned for the phase II part of patients with BRAF V600 mutant mCRC, when 50% of the total sample size (14 patients) have completed four cycles of treatment, to allow stopping early for futility when there is no treatment effect.

[figure not shown]
Note that obvious corrections will be made at the time of analysis to address minor formatting or spelling mistakes present in the SAP without the need to amend this document.

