Table 1-1Objectives and related endpoints

Objective	Endpoint

Primary	
Phase Ib: To estimate the MTD(s) and/or RP2D(s) of oral LGX818 in combination with oral MEK162, and of oral LGX818 in combination with oral MEK162 and oral LEE011 in patients with BRAF V600- dependent advanced solid tumors	Phase lb: Incidence of Dose Limiting Toxicities
 Phase II: To assess clinical efficacy of the LGX818 and MEK162 dual combination and LGX818 and MEK162 and LEE011 triple combination in the respective Phase II populations: Arm 1: metastatic BRAF V600 mutant mCRC patients (dual combination) Arm 2: metastatic BRAF V600 mutant melanoma patients who have progressed after prior selective BRAFi treatment (dual combination) Arm 3/ Arm A: metastatic BRAF V600 mutant melanoma patients who are naïve to prior selective BRAFi treatment (dual and triple combination). 	Phase II arm 1: Disease control rate (DCR) as per RECIST v1.1 Phase II arms 2 and 3 / Phase II arm A: Objective Response Rate (ORR) as per RECIST v1.1
Secondary	
Phase lb + II: To characterize the safety and tolerability of LGX818 and MEK162 in combination, and LGX818 and MEK162 and LEE011 in combination	Phase lb + II Incidence and severity of AE
Phase lb To determine the single and multiple dose PK profile of the LGX818 and MEK162 combination, and of the LGX818 and MEK162 and LEE011 combination To assess preliminary clinical anti-tumor activity of the LGX818 and MEK162 combination, and of the LGX818 and MEK162 and LEE011 combination	Phase lb Time vs. plasma concentration, basic PK parameters of LGX818 and MEK162 and LEE011 and known active metabolite(s) ORR as per RECIST v1.1
Phase II To further assess clinical efficacy of the LGX818 and MEK162 dual combination and of the LGX818 and MEK162 and LEE011 triple combination in the Phase II populations	Phase II Progression free survival (PFS), time to response (TTR), duration of response (DOR) as per RECIST v1.1, and Overall Survival (OS)

To characterize baseline molecular status of

molecules relevant to RAF/MEK/ERK and

EFGR/ PI3K/AKT signaling in tumor tissue

Baseline molecular status (mutation/amplification/expression) in tumor tissue of potential predictive markers of tumor response or resistance (BRAF, HRAS, KRAS, NRAS, PTEN, cKIT, PIK3CA, MAP2K1, MAP2K2, ARAF, c-MET, RAF1, EGFR)

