2.1.2.9 Scheduled study visit and window for the analysis

In order to summarize longitudinal data per time point, assessments will be allocated to visits using predefined time windows. Unless otherwise specified, when more than one assessment is available for a visit, all assessments will be listed under the visit while only the assessment closest to the planned day for the visit will be used for summaries and analyses.

Time windows are provided in Table 2-1.

Assessment	Visit	Time Window	Planned Visit Timing	Time Window Definition
Efficacy Assessm	nents		-	
Tumor response for imaging assessments	Screening	Baseline	Pre- treatment	D-42 to D-1 for whole body bone scans D-21 to D-1 for all other image scans
	C1D28	Between week 3 and week 4 ± 3 days	C1D28	D18 to D31
	C2D28 C4D28	C2D28 ± 7 days C4D28 ± 7 days	D56 D112	D49 to D63 D105 to D119
	every 8 v	,	ease progressio	n, i.e. C6D28, C8D28
	EOT	EOT + 14 days± 3 days		
Biomarkers				
Tumor Biopsy Sam	ples			
Fresh tumor biopsy	Screening	Baseline	Pre- treatment	D-14 to D-1
	C1D8 or	C1D8 ± 3 days or	D8 or	D5 to D11 or
	C1D16	C1D16 + 5 days± 3 days	D16	D13 to D24
	relapse			
CCI				

C = cycle, D = Day, 01 = start of study treatment

All other assessments (i.e. laboratory evaluations etc.) the reported visit will be used

Assessment	Visit	Time Window	PK assessment time point	Time Window Definition
Phase lb (Dose	C1D1	-03:00	< 00:00 pre-dose	C1D1, [-03:00, 00:00]
escalation)	C1D1	± 00:05	00:30 post-dose	C1D1, [00:25, 00:35]
	C1D1	± 00:15	01:30 post-dose	C1D1, [01:15, 01:45]
	C1D1	± 00:30	02:30 post-dose	C1D1, [02:00, 03:00]
	C1D1	± 00:30	04:00 post-dose	C1D1, [03:30, 04:30]
	C1D1	± 01:00	06:00 post-dose	C1D1, [05:00, 07:00]
	C1D1	± 01:00	08:00 post-dose	C1D1, [07:00, 09:00]
	C1D2	-03:00	< 00:00 pre-dose	C1D2, [-03:00, 00:00]
	C1D15	-03:00	< 00:00 pre-dose	C1D15, [-03:00, 00:00]
	C1D15	± 00:05	00:30 post-dose	C1D15, [0:25, 00:35]
	C1D15	± 00:15	01:30 post-dose	C1D15, [01:15, 01:45]
	C1D15	± 00:30	02:30 post-dose	C1D15, [02:00, 03:00]
	C1D15	± 00:30	04:00 post-dose	C1D15, [03:30, 04:30]
	C1D15	± 01:00	06:00 post-dose	C1D15, [05:00, 07:00]
	C1D15	± 01:00	08:00 post-dose	C1D15, [07:00, 09:00]
	C1D16	-03:00	< 00:00 pre-dose	C1D16, [-03:00, 00:00]
	C2D1	-03:00	< 00:00 pre-dose	C2D1, [-03:00, 0:00]
	every c	ycle Day 1 (pre	e-dose), up to Cycle 10 C10D1), i.e. C3D1, C4D1,,
Phase II arm 2 +	C1D1	-03:00	< 00:00 pre-dose	C1D1, [-3:00, 000:00]
Phase II arm 3	C1D1	± 00:05	00:30 post-dose	C1D1, [0:25, 000:35]

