2.2 Analysis sets

For inclusion in any analysis set it is required that a patient has correctly consented and has received at least one dose of study treatment. For those incorrectly consented patients, they will be excluded from all analysis.

The following analysis sets which will be derived prior to database lock will be used.

Full Analysis Set

The FAS includes all patients who received at least one dose of LGX818 or MEK162 or LEE011. Patients will be classified according to the planned treatment regimen (dose, schedule, tablet variant). The FAS will be used for all listings of raw data. Unless otherwise specified the FAS will be the default analysis set used for all analyses.

Note that patients who were screened and are eligible but never started treatment will not be included in the FAS. This is considered as an acceptable deviation from the ITT principle in the context of the Phase I study in which safety is considered as a primary objective.

The FAS will be used for all listings of raw data. Unless otherwise specified the FAS will be the default analysis set used for all analyses. Patients will be analyzed according to the planned treatment regimen.

Safety Set

The safety set includes all patients who received at least one dose of LGX818 or MEK162 or LEE011, and have at least one valid post-baseline safety assessment. The statement that a patient had no AEs (on the AE eCRF) constitutes a valid safety assessment.

Patients will be classified according to treatment received (See Section 2.1.1.2).

Dose Determining Set (DDS)

The dose-determining set (DDS) includes all Phase Ib patients from the safety set who either completed a minimum exposure requirement and have sufficient safety evaluations or discontinued prematurely due to a dose limiting toxicity (DLT).

A patient is considered to have met the minimum exposure requirement if having received at least 75% of the planned combination doses (i.e. 21 out of 28 planned daily doses for QD or BID, 11 out of 14 planned doses for an every other day dosing schedule, and 16 days out of 21 days for 3 week on, 1 week off dosing schedule) of study treatment within the first Cycle of dosing. The length of a cycle is 28 days.

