3.4.2.2 Phase II

Efficacy will be assessed using the local CT/MRI assessments evaluated under RECIST v1.1. The Best Overall Response (BOR) for each patient and individual lesion measurements will be listed. The BOR will be summarized using the Disease Control Rate (DCR) for Phase II arm 1 and the Objective Response Rate (ORR) for Phase II arms 2 + 3 and Phase II arm A.

- The ORR is defined as the proportion of patients with a BOR of CR or PR.
- The DCR is defined as proportion of patients with a BOR of CR or PR or SD.

Both confirmed and unconfirmed summaries will be provided.

Patients who withdrew prematurely due to progression of disease without having any postdose tumor assessment will be classified as treatment failures. Similarly, patients who died due to their disease without having any post-dose tumor assessment will be classified as treatment failures.

ORR and DCR will be provided with their corresponding 95% exact confidence interval according to Clopper-Pearson method [Clopper and Pearson 1934].

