3.5.1.1 Best overall response and other binary endpoints

Best overall response

The Best overall response (BOR) is the best response recorded from the start of the treatment until disease progression/recurrence.

Only overall tumor assessments reported by investigator and performed before the start of any further anti-neoplastic therapies (i.e., any additional secondary anti-neoplastic therapy or surgery) will be considered in the assessment of best overall response.

Confirmation of complete and partial responses (CR and PR, respectively) must be made at least 4 weeks apart. Stable disease must occur > 6 weeks after the start of treatment.

Version 2.2

Confidential

Patients who are of unknown clinical response will be treated as non-responders.

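### The Arm 1 primary DCR is declared at week 16 in SAP section 3.4.1.2 but analysed as best overall response with no time point in sections 3.4.2.2 and 3.5.1.1

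*SAP*

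**What the plan says.** Four places in the SAP bear on the Arm 1 (mCRC) primary endpoint.

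- Section 3.4.1.2 names the variable and its time: "For arm 1, the primary variable is the Disease Control Rate (DCR) at week 16".
- Section 3.4.2.2 gives the analysis. It applies the DCR to Arm 1 by name, defines it without a time point ("The DCR is defined as proportion of patients with a BOR of CR or PR or SD"), and attaches a 95% Clopper-Pearson interval.
- Section 3.5.1.1 sets the period and the minimum time for SD: "The Best overall response (BOR) is the best response recorded from the start of the treatment until disease progression/recurrence", and "Stable disease must occur > 6 weeks after the start of treatment".
- Table 1-1 (section 1.2) lists "Phase II arm 1: Disease control rate (DCR) as per RECIST v1.1", again without a time point.

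Section 1.4, which declares departures from the protocol, mentions only the move from a Bayesian to a frequentist analysis. It declares no change to the timing of the DCR.

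**The concern.** The section that names the primary variable and the section that analyses it do not describe the same quantity on a plain reading. A patient with SD at the week 8 scan and progression at the week 16 scan is a success under sections 3.4.2.2 and 3.5.1.1, but is not under disease control at week 16.

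No rule in the SAP says how status at week 16 is to be derived: which scan is used, what happens if it is missing, or how early SD followed by progression is classed. Two programmers working from this SAP could report different primary results for the arm. The Bayesian estimation has been dropped and no test replaces it, so the observed rate and its interval are the whole primary result for Arm 1. Its definition therefore needs to be unambiguous.

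**Working it through.** The SAP states no null or target DCR, error rate or power for Arm 1, so it has no figure of its own to reproduce. The check covers timing, then logic, then an illustration of size.

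**1. Is week 16 a real time point in this design?**
- Section 2.2: "The length of a cycle is 28 days". Four cycles are 4 × 28 = 112 days, and 112 / 7 = 16 weeks.
- Table 2-1 plans the C4D28 scan at D112. Its windows for C2D28 and C4D28 read "D49 to D63 D105 to D119".
- Section 1 planned the Arm 1 interim look "when 50% of the total sample size (14 patients) have completed four cycles of treatment", which is also 16 weeks.

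Week 16 therefore matches both a scheduled scan and the planned interim criterion. It is not a stray phrase.

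**2. Which scan first allows SD to count under section 3.5.1.1?**
- The threshold is more than 6 × 7 = 42 days.
- The C1D28 window (D18 to D31) is too early.
- The C2D28 window (D49 to D63, about week 8) lies wholly after day 42, so one SD at that scan is enough for a BOR of SD.

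**3. Direction, with week 16 read as status at that time.**
- Anyone in CR, PR or SD at about D112, without earlier progression or new antineoplastic therapy, has a BOR of at least SD. Every week-16 success is therefore a BOR success.
- The reverse fails for a patient with SD at week 8 who progresses by week 16.
- So the BOR-based DCR is at least the week-16 DCR. This step needs no distributional assumption.

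**4. Size (illustration only; the SAP gives no PFS figure for Arm 1).** Assume a constant hazard of progression or death, so S(t) = 0.5^(t / median), with 30.4375 / 7 weeks per month. Take S(8 weeks) as the BOR-based rate and S(16 weeks) as the week-16 rate.

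| Assumed median PFS | S(8 wk) | S(16 wk) | Gap |
|---|---|---|---|
| 2 months | 0.529 | 0.279 | 0.250 |
| 3 months | 0.654 | 0.427 | 0.227 |
| 4 months | 0.727 | 0.529 | 0.198 |
| 5 months | 0.775 | 0.600 | 0.175 |
| 6 months | 0.809 | 0.654 | 0.155 |

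Under this model S(16) = S(8)², so the gap is S(8) × (1 − S(8)), which cannot exceed 0.25.

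**5. What that means for the reported interval.** The interim fraction implies a planned size of 14 / 0.5 = 28. With an assumed 12-week median, S(8) = 0.630 and S(16) = 0.397. The expected counts are 28 × 0.630 = 17.6 and 28 × 0.397 = 11.1. Rounded, with Clopper-Pearson limits:
- 18/28 = 64% (95% CI 44% to 81%);
- 11/28 = 39% (95% CI 22% to 59%).

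The actual Arm 1 number is below the planned one, because the arm was terminated early, and this SAP does not state it.

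**The case against.** **The sections can be read as complementary.** Section 3.4.1.2 would supply the time point and section 3.4.2.2 the response categories and interval method, giving one endpoint with an unfinished derivation. Alternatively, week 16 could mean BOR up to week 16. On that reading the patient with SD at week 8 and progression at week 16 is a success in both sections, and the gap largely disappears. This stands as a limit: the direction and size above are conditional on reading week 16 as status at that time. It does not clear the text, because the SAP states neither alternative and section 3.5.1.1 runs BOR to progression without stopping at week 16.

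**The protocol may settle it.** Section 1.3 defers to the protocol's data analysis section, and the protocol is not at hand. The SAP still has to agree with itself, and section 1.4 declares no change of time point.

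**Little now depends on it.** Section 2.3 records that Arm 1 was terminated early and its interim analysis dropped. Section 1 limits the final analysis to the outputs in section 4, where the only BOR summary table (14.2.1.1d) is for the triple combination. This stands and lowers the severity. What remains is the initial interim CSR, which section 1.5 says this SAP describes and which contains the dual-combination outputs.

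**Stronger inferences a reader might draw.** One is that a BOR-based rate was or will be presented under a week-16 label. No Arm 1 DCR table title or shell appears in the document, so this is unsupported. Another is that the reported DCR is inflated by 15 to 25 points. That range rests on assumed medians and an assumed exponential form, not on any figure in the SAP.

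**Conclusion.** The inconsistency is real as written. The Arm 1 primary variable carries a week-16 time point in section 3.4.1.2 and none in section 3.4.2.2, section 3.5.1.1 or Table 1-1, and nothing in the SAP reconciles them.

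If week 16 means disease status at that time, the BOR-based rate is equal to or higher than the declared endpoint by logic alone. The amount is not in the document; it is about 15 to 25 percentage points under exponential PFS with medians of 2 to 6 months.

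Severity is moderate. It concerns the definition of a primary endpoint, but in an arm that closed early, with no test or decision rule attached and no Arm 1 DCR table in the final-CSR list.

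**What to change.** State one Arm 1 primary DCR in the same terms in Table 1-1, section 3.4.1.2 and section 3.4.2.2:

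- **Success:** the FAS patient is in CR, PR or SD at week 16 (C4D28), with no earlier progression, death or new antineoplastic therapy.
- **Week-16 scan missing or out of window:** a later scan still showing CR, PR or SD counts as control; otherwise the patient is a failure. Failing everyone without a scan in D105 to D119 would wrongly fail patients whose control is documented afterwards.
- **BOR-based DCR:** keep it, labelled as supportive.
- **Initial interim CSR:** if the Arm 1 DCR reported there used BOR, add the week-16 figure with its Clopper-Pearson interval.

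The cost is a wording change and one derivation from scans already scheduled; Listing 16.2.6.1 already shows overall response by assessment. The stated rate may come out lower than the BOR-based one.
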